Imagery Vividness	Vividness of Movement Imagery Questionnaire (VMIA-2)	A 12-item questionnaire where participants rate each mental image in 3 ways (internal visual imagery, external visual imagery, and kinesthetic imagery) from 1 (perfectly clear and vivid) to 5 (no image at all)	x	x	x
Imagery Ability	Movement Imagery Questionnaire (MIQ-3)	A 12-item questionnaire to assess an individual's ability to image four movements using internal visual imagery, external visual imagery, and kinesthetic imagery.	x	x	x
Weight Bias	Weight Bias Internalization Scale Modified (WBIS-M) ⁵⁷	An 11-item survey that measures the degree to which people apply weight-based stereotypes to themselves and base their self-evaluations on weight.	x	x	x
Body Dissatisfaction	Figure Rating Scale (FRS)	A 2-item survey that asks participants to rate their current body size and ideal body size.	x	x	x
Identity	Physical Activity Identity	A 4-item survey that asks about participant's physical activity identity	x	x	x
Physical Activity Habit Strength	Self-Report Index of Habit Strength (SRHI)	Involves 12-items that assesses habit strength of physical activity.	x	x	x
Diet	3-day Diet Record	Record food intake over 3 days (including 1 weekend day)	x	x	x
COVID-19 Tracking	Survey	A brief survey that asks about whether COVID-19 impacted participation in the study	x		x
Anthropometrics	Body Weight	Digital scale accurate to ± 0.1 kg	x	x	x
	Waist Circumference	Measured with a tape measure just over the iliac crest.	x	x	x
	Height	Measured with a stadiometer in cm	x		x
Cardiovascular Markers	Blood Pressure	Automatic sphygmomanometer (average of 2 seated values taken after 5 min rest)	x	x	x
	Cardiorespiratory Fitness	Estimated using the YMCA 3-minute step test protocol ⁵⁸	x	x	x

Note: All proposed quantitative measures have demonstrated adequate reliability and validity
 *Focus groups and interviews will also be used to explore feasibility

B. Description of Population to be Enrolled:

B.1 Patient and Provider Partners: Two types of partners (n=10 total) will be recruited, applying strategies learned from participatory and research partner-engaged research methods:

1. Adult participants with overweight or obesity seeking weight loss and/or improvements in health and well-being (n=9)

2. Providers, including Registered Dietitians (RDs) with experience delivering weight loss or lifestyle intervention curriculum (n=1)

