We will enrich recruitment of minority participants above the Denver metro proportions⁵⁹ (target ≥15% Black, ≥30% Hispanic). A sample size of n=10 was chosen because ~10 research partners/cycle identify 95% of design issues.⁶⁰ Special classes of participants considered vulnerable populations will not be included in the study. Our primary recruitment strategy for this study will be university emails, recruitment from existing behavioral weight loss interventions (for participant partners), and through personal invitations (for RDs).

B.2 Eligibility Criteria: Eligibility criteria are designed to select a broad range of participant partners with overweight and obesity (women and men) for whom a physical activity program would be appropriate.

To be eligible to participate in this research, volunteers must meet the following criteria:

Inclusion Criteria:

- For all types of research partners:
 - Men and Women
 - Age 18-65 years
 - Have access to a computer and/or smart phone, and Wi-Fi
 - Speak English
- For the participant partners only:
 - Body Mass Index 25-45 kg/m²
 - Insufficiently active (defined as <150 min/week of voluntary exercise at moderate intensity over the past 3 months)
 - Willing not to enroll in any other formal weight loss, physical activity program, or fitness center membership over the next 5 months.
 - Have a primary care physician (or has access to a healthcare professional and/or are willing to establish care with a primary care physician prior to study enrollment) to address medical issues which may arise during screening or study procedures/interventions.
 - Capable and willing to give informed consent, understand exclusion criteria, attend the *Move+* program sessions, and complete outcome measures.
- For the provider partners only:
 - >1 year experience with delivering lifestyle interventions involving changes in diet and/or exercise behaviors.

Exclusion Criteria

- For participant partners:
 - Considered high risk, based on the American College of Sports Medicine Guidelines for Exercise Testing and Prescription⁶¹ (i.e. have CVD symptoms or known CVD, diabetes, or end-stage renal disease).
 - Females who are currently pregnant or lactating, were pregnant within the past 3 months, or planning to become pregnant in the next 5 months will also be excluded
 - Self-reported cardiovascular disease:
 - Cardiac, peripheral vascular, or cerebrovascular disease
 - Self-reported symptoms suggestive of cardiovascular disease:

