Online Fitness Membership	
 Choice in PA type: cardio, strength and conditioning, yoga, meditation Opportunities for social support from other fitness members 	Autonomy, Relatedness	Participants access online
Guided Imagery	
 Weekly 3-5 min recorded sessions Mental images of a positive, fun PA experience⁴⁶ and moving with confidence 	Autonomy, Competence	Trained* RD provides online access to recordings to participants

*Training will ensure RDs provide an autonomy-supportive environment and are confident in teaching PA content

C.2.2 Delivery of Move+ Program: 10 research partners (9 patients, 1 RDN) will complete a single-arm 12-week field trial, where an RDN delivers ≥1 Move+ session per week (group-class, 1:1, and/or guided imagery), remotely. Patients will receive a 12-week online fitness membership, using the option with the highest acceptability from Aim 1 Phase 1 (COMIRB # 22-0147). Research partner recommendations will be used to refine intervention components. Research partners will be compensated for their time in completing the 12-week single-arm field trial and the quantitative and qualitative measures. See Table 3 below for the schedule of delivery of components.

Table 3. Schedule of Delivery of Move+ Program Components

Program Component	Intervention Week												
	0	1	2	3	4	5	6	7	8	9	10	11	12
Introduction to the Study	x												
Group-Based Class		x			x				x				
Individualized Support Session				x			x				x		
Guided Imagery Sessions		x	x	x	x	x	x	x	x	x	x	x	x
Access to Online Fitness Center Membership	x	x	x	x	x	x	x	x	x	x	x	x	x

C.2.3 Physical Activity Prescription:

Participants will receive a recommendation to gradually increase moderate intensity PA to 150 min/week over the initial 12 weeks. This target is consistent with current PA guidelines for overall health^{67, 68}. Participants will be instructed in how to use a relative intensity scale⁶⁷ to achieve the target moderate intensity.

D. Description, Risks and Justification of Procedures and Data Collection Tools:

Screening:

Description: See detailed description in Section C.1 above.

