Qualitative Data:

Description: At the end of the 12-week field trial participant partners will be asked to participate in a 90-minute semi-structured focus group, and the RD partner will be asked to participate in a 60-minute semi-structured interview. The focus group and interview will be conducted remotely, via Zoom Videoconferencing, a web conference software with full HD video and audio capability, or in-

person. Zoom has wireless sharing, enabling users to access the platform via desktop or mobile device. Participants will have the option to connect to audio via phone or computer and can use their real name or a nickname or alias during the interview discussion to protect their privacy. Use of a web camera will be optional, with the understanding that it could reduce privacy. During the focus group or interview process, we will make every effort to protect subject privacy by only using first names in the group discussion. Any names included in the transcription will be changed to a de-identified study ID. The identity of subjects and the data acquired as a result of this study will be treated with professional standards of confidentiality. Only members of the research team will have access to information collected from the participants.

Digitally recorded interview data will be sent to an outside company to be transcribed verbatim. Once we have verified the written documents, the recordings will be deleted. The typed transcriptions will be kept on a password-protected university server and any printed copies will be kept in a locked file cabinet in [name] locked office. Data records will be maintained for at least 5 years after the publication of results. At that time, the PI may destroy the data records by deleting them from electronic media and by shredding paper documents, but some of the data records may be retained indefinitely.

Sharing of data among investigators within the institution is typically facilitated either by providing a password for the database or by electronic transmissions. All members of the research group have individual computers that are part of the institution network with institutional oversight of security. Files that contain data that could jeopardize blinding to treatment code are password-protected to restrict access. Electronic transfer, in a manner that is compliant with regulations, typically facilitates sharing of data with investigators or monitoring personnel outside the institution.

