Semi-structured Focus Group: Topics that will be addressed in this focus group include participant experience with the *Move+* program including feasibility/acceptability of each *Move+* intervention component, assessment of cultural relevance, and feedback to refine *Move+* components. Additional topics include facilitators and barriers for receiving the *Move+* program. The study team will make decisions on the final *Move+* program content based on research partner feedback. Thus, the final *Move+* program content will reflect the wants and needs of the research partners. We will code for research partner comments that would result in a revision within each transcript. We will discuss all potential revisions within our study team meetings and collectively decide on which revisions to make outright, which revisions to develop a prototype for and go back to research partners for input, and which revisions to discard. As a study team, we will ensure that all revisions made to the program features are aligned with retain fidelity of the Self-Determination Theory.

Semi-structured 60-minute Interviews: Topics that will be addressed in this focus group include RD experience with delivering the *Move+* program including feasibility/acceptability of each *Move+* intervention component, assessment of cultural relevance, and feedback to refine *Move+* components. Additional topics include facilitators and barriers for delivering the *Move+* program.

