- **Feasibility of Intervention Measure (FIM):** At the end of the 12-week field trial, research partners will be asked to evaluate each *Move+* component using the FIM⁵¹ with a 1-5 Likert scale (1=Completely Disagree, 5=Completely Agree). The FIM is a 4-item questionnaire that asks partners about whether the intervention component seems implementable, seems possible, seems doable, and seems easy to use. The FIM demonstrated strong psychometric properties including content validity,

discriminant content validity, reliability, structural validity, structural invariance, known-groups validity, and responsiveness to change.

- **Weekly Survey:** Every week during the 12-week field trial, patient partners will be asked to rate their satisfaction with specific program components that they received using a 1-10 Likert scale (1=Strongly Dislike, 10=Strongly Like), to describe their engagement with the virtual fitness membership and rate the classes they tried, and to provide any input for refinement/improvement.
- **Net Promoter Score (NPS):** At the end of the 12-week field trial, research partners will be asked to evaluate each *Move+* component using the NPS. The NPS is a single question with a 1-10 Likert scale: How likely is it that you would recommend the *Move+* component to a friend or colleague? Respondents are grouped as follows: 1) promoters (score 9-10) are loyal enthusiasts who will keep referring others and fueling growth, 2) passives (score 7-8) are satisfied but unenthusiastic customers who are vulnerable to competitive offerings, and 3) detractors (score 0-6) are unhappy customers who can impede growth with negative word-of-mouth. The final NPS score is calculated as % promoters - % detractors. NPS scores range from -100 to +100, with scores >0 indicating good acceptability.
- **Perceived Characteristics of Intervention Scale (PCIS):** At the end of the 12-week field trial, the RD partner will be asked to complete the PCIS (e.g., completed in both phases 1-2). The PCIS is a 20-item scale that measures trialability, relative advantage, compatibility, complexity, potential for intervention adaptation, etc. The PCIS is a reliable measure of perceived characteristics of interventions, with some preliminary support for its validity.⁵² Participant partners will not be asked to complete this scale.

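### Does the 95% rationale for ten research partners need limiting because only one of the ten is a provider?

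*Combined protocol and SAP*

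**What the plan says.** B.1 (Patient and Provider Partners) recruits two kinds of research partner: adults with overweight or obesity (n=9) and providers (n=1). The only justification for the total is "A sample size of n=10 was chosen because ~10 research partners/cycle identify 95% of design issues", supported by a literature citation. Section C.2.2 repeats the split: "10 research partners (9 patients, 1 RDN) will complete a single-arm 12-week field trial". Table 1 has the same two columns.

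The data sources divide partly by role. In section D (Qualitative Data), participants attend a focus group and "the RD partner will be asked to participate in a 60-minute semi-structured interview". The focus group entry says "Additional topics include facilitators and barriers for receiving the" program; the RD interview entry says "Additional topics include facilitators and barriers for delivering the" program. Two questionnaires, the PCIS and the OR4KT, go to the RD only. The PCIS entry states "Participant partners will not be asked to complete this scale", and the OR4KT entry says the same. The PCIS entry also notes that it is "completed in both phases 1-2". Under F.1, a PCIS scale score below 3 or an average Net Promoter Score below 0 marks an area for refinement. F.1 attaches no such rule to the OR4KT.

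**The concern.** The number ten is reached only by adding two roles that see different things. If a problem can be met only by the person running the sessions, nine of the ten partners cannot report it. The relevant count is then 1, not about 10. B.1 places no limit on the 95%, so a reader could carry it over to delivery problems, where it has no basis.

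Delivery is also part of what this phase refines. F.3 aims for a package that suits organizations as well as participants, and section IV says the results will inform a later pilot feasibility trial. The risk would be a manual taken forward in the belief that nearly all delivery problems had been found, when one person's experience had been sampled.

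**Working it through.** **Inputs.** Participants 9, providers 1, total 9 + 1 = 10 (B.1, C.2.2, Table 1). Stated yield: 95% with about 10 partners per cycle (B.1). Detection probability per partner: not given anywhere.

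**Can the 95% be reproduced?** Not independently. The usual problem-discovery formula gives the chance that at least one of n partners meets an issue as 1 − (1 − p)^n, where p is the chance for one partner. It assumes equal p, independent partners, and that every partner can meet the issue. Setting 1 − (1 − p)^10 = 0.95 gives p = 1 − 0.05^(1/10) = 0.259. Putting that p back in returns 95% at n = 10 by construction, so it confirms nothing.

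**What the formula says about one provider.** At n = 1 it reduces to p itself.

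| Assumed p | n = 10 | n = 9 | n = 1 |
|---|---|---|---|
| 0.10 | 65.1% | 61.3% | 10% |
| 0.20 | 89.3% | 86.6% | 20% |
| 0.259 (back-solved) | 95.0% | 93.3% | 25.9% |
| 0.50 | 99.9% | 99.8% | 50% |

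One provider reaches 95% only if p is at least 0.95. The direction is therefore clear, but every entry rests on an assumed p. None should be read as the share of delivery problems this study will find.

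**How large is the provider-only set?** The two entries in section D compare as follows.

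- Shared by focus group and RD interview: how feasible and acceptable each component is, cultural relevance, and suggestions for refinement.
- Different: only the closing sentence of each entry, on receiving versus delivering the program.
- PCIS: RD only, and tied to a refinement rule in F.1.
- OR4KT: RD only, but it measures organizational readiness. It does not measure faults in the design of Move+, so it lies outside what the B.1 sentence is about.

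The unsupported area is thus the delivery part of one interview plus the PCIS.

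**What else reaches that area?** The PI reviews session recordings against a checklist (Table 1, Fidelity and Adaptations). The PCIS was also used in Phase 1, though this document does not say with how many providers. Prototypes may go back to partners (section D, Semi-structured Focus Group), and design options may be re-surveyed for up to 4 cycles (REDCap Survey on Design Features). These add observation and rounds of input, but no second provider in this phase.

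**Does anything depend on the 95%?** No. F.1 is descriptive apart from exploratory paired t-tests on outcome changes. F.2 and F.3 code and integrate whatever is reported. Under section D, comments that would lead to a revision are coded in each transcript and discussed by the team, so a single remark from the RD can prompt a revision. No step takes the detection percentage as an input.

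**The case for a change.** The best case for acting is that the sentence is the sole rationale for the sample size, carries no qualification, and could be made accurate with one clause at almost no cost. Disclosing that there is one RD does not by itself limit the 95%. The PCIS rule in F.1 speaks of average scores, yet in this phase the average is one person's answer.

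Much of this stands. The rule does not support 95% for issues that only a provider can observe, and n=1 has no justification of its own. What does not stand is the step to a needed change. The plan does not assert the figure by partner type, so the clause would deny a claim that was not made. Whether the cited rule extends to mixed groups of users depends on a source that cannot be consulted here. As for the PCIS, its own entry already says that the RD completes it and participants do not, so any competent report will present it as a single respondent's score.

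**Conclusion.** No change is needed. The point is true but narrow: 1 provider respondent against the roughly 10 in the cited rule, affecting only delivery issues invisible to participants and to the PI's review of recordings. It corrects no figure and leaves recruitment, data collection, thresholds, analyses and conclusions as they are. For a descriptive, single-arm refinement study of ten people, having one RD deliver the program is a fair trade-off and is openly stated. If B.1 is being edited anyway, the authors could add that the 95% is not claimed for provider-only issues; that is a matter of wording.

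This conclusion assumes that the 95% sentence refers to the pooled partners, as B.1's definition of the two partner types indicates, and that PCIS results will be reported as one person's ratings. It does not depend on any value of p, and it takes no view on whether 95% holds for issues participants can observe.

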Justification and Risks: The primary risk from screening measures is diagnosis of a previously unknown disease. If a previously undiagnosed disease is found during screening or during any of the procedures, the PI will contact the participant and discuss the diagnosis and its ramifications, and when appropriate, the volunteer will be referred to their Primary Care Provider.

Move+ Program and Exercise Prescription:

Description: See detailed description in Section C.2 above.

Justification and Risks: The exercise prescription is part of current guidelines for overall health. Subjects will receive a recommendation to gradually increase moderate intensity PA to 150 min/week over the 12 weeks. This target is consistent with current PA guidelines for overall health^{67, 68}. Subjects will be provided an outline of weekly PA goals (min/week) to gradually progress to the target of 150 min/week by week 12. Subjects will be instructed in the use of a relative intensity scale to achieve the target intensity as outlined in current PA guidelines⁶⁷ (moderate-intensity activity defined as a level of effort of 5 or 6 on a scale of 0 to 10, where 0 is the level of effort of sitting, and 10 is maximal effort). The primary risks associated with beginning an exercise program are likely to be fatigue, shortness of breath, or muscle soreness during or after the training sessions. It is expected that when these symptoms occur, they will be minor and brief. During exercise there is a small risk subjects may experience musculoskeletal injuries. During exercise there is a small risk subjects may trip or fall. During exercise there is a very small risk subjects will experience cardiovascular symptoms such as chest pain, shortness of breath, dizziness, syncope, or lower extremity claudication.

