- Risks of the exercise program will be minimized by ensuring all subjects meet the specific inclusion/exclusion criteria. Subjects will have previously undergone a medical screening including medical history interview and physical exam, and assessment of blood pressure. According to the most recent American College of Sports Medicine (ACSM) Guidelines for Exercise Testing and Prescription⁶¹, exercise stress testing prior to initiation of moderate or vigorous exercise is only indicated for high-risk individuals (i.e. individuals with symptoms of CVD or individuals with known CVD, diabetes, pulmonary disease, or end-stage renal disease). Subjects with these conditions are excluded from our study, thus all subjects in our study will be classified as low- or moderate-risk by ACSM guidelines and thus routine screening exercise stress testing prior to exercise initiation is not recommended.
- If subjects experience muscle soreness, we will prescribe light stretching, and hot/cold therapy to reduce the soreness. If these approaches do not alleviate the soreness, we will advise the use of OTC pain relievers (e.g., aspirin, acetaminophen, ibuprofen), unless contraindicated. It is anticipated that some subjects will experience soreness during the first few days of exercise, but since the recommended intensity is moderate we expect the symptoms will be minor and transient.
- Although some minor to moderate orthopedic injuries may occur during the exercise program (primarily lower body musculoskeletal injuries such as muscle sprains, tendonitis, shin splints) given the moderate intensity and gradual increase of the exercise prescription we do not expect any severe injuries. Subjects who experience minor to moderate orthopedic injuries will be allowed to remain in the study and return to exercise as tolerated.
- Participants may feel uncomfortable about answering questions that are being asked group-based classes or individualized support sessions. Participants are not required to answer any questions. To minimize this risk, we will notify participants that they are not required to answer any questions and that they may choose to leave the interview at any time. In addition, participants can ask to pause the recording at any time. Lastly, we will allow participants to send a chat privately to the interview moderator if they want to write down any thoughts or reactions that they would prefer not to share out loud, or that they didn't have a chance to say.

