Description: A TMST will be obtained as a surrogate measure of cardiorespiratory fitness. In accordance with the YMCA TMST protocol⁵⁸ participants will step on and off a 30.5 cm (12 inch) step 24 times per minute for 3 minutes. They will be aided by an electronic metronome set at 96 beats per minute which they are to match with 96 steps (24 ascent-descent cycles) per minute. At one-minute intervals participants will be told "you are doing well" and the time remaining was indicated. Immediately after completion of the test participants rate their perceived exertion using the Borg (6 to 20) perceived exertion scale. Their cumulative heart rate will be determined by auscultation with a stethoscope during the first minute after test completion.

Justification and Risks: The TMST predicts 50-90% of the variance in fitness as assessed by exercise treadmill V02 max testing and is thus an inexpensive surrogate for cardiorespiratory fitness, an important metabolic outcome measure. The TMST is also recommended by the ADOPT working group as an important predictor of response within weight loss interventional studies. The primary risks associated with the TMST are likely to be fatigue, shortness of breath, or muscle soreness during or after the test. It is expected that when these symptoms occur, they will be minor and brief. During the TMST there is a small risk subjects may experience musculoskeletal injuries. During the TMST there is a small risk subjects may trip or fall. During the TMST is a very small risk subjects will experience cardiovascular symptoms such as chest pain, shortness of breath, dizziness, syncope, or lower extremity claudication. Study staff will monitor the test and the test will be stopped if subjects experience any of these symptoms and subjects will be referred to their PCP or to the emergency room for further evaluation depending on the severity of symptoms. Risks of the TMST will be minimized by ensuring all subjects meet the specific study inclusion/exclusion criteria. Subjects will have previously undergone a medical screening including medical history interview and physical exam, and assessment of blood pressure.

D. Potential Scientific Problems:

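### Injuries, falls and symptoms that the protocol names as exercise risks are not systematically collected or summarised during the 12 weeks of home exercise

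*Combined protocol and SAP*

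**What the plan says.** **Exposure.** Section C.2.2 states that "10 research partners (9 patients, 1 RDN) will complete a single-arm 12-week field trial". Section D (Move+ Program and Exercise Prescription) adds: "Subjects will receive a recommendation to gradually increase moderate intensity PA to 150 min/week over the 12 weeks". Sessions are delivered by videoconference, and for the fitness membership Table 2 gives the delivery mechanism as "Participants access online".

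**Named risks.** The same part of section D lists fatigue, shortness of breath, soreness, trips and falls. It also says: "During exercise there is a small risk subjects may experience musculoskeletal injuries". On the heart and circulation it says: "During exercise there is a very small risk subjects will experience cardiovascular symptoms such as chest pain, shortness of breath, dizziness, syncope", and the sentence ends with claudication.

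**Stated responses in home exercise.** There is a stepwise response to soreness. For injury: "Subjects who experience minor to moderate orthopedic injuries will be allowed to remain in the study and return to exercise as tolerated".

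**Stated response in the step test.** For the same five cardiovascular symptoms, section D (3 Minute Step Test) says: "Study staff will monitor the test and the test will be stopped if subjects experience any of these symptoms", followed by referral according to severity.

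**Repeated data collection.** Under Outcome Questionnaires, the Weekly Survey reads: "Every week during the 12-week field trial, patient partners will be asked to rate their satisfaction with specific program components". It also asks about engagement with the membership, ratings of classes tried, and any input for improvement.

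**The concern.** The protocol expects certain events and says what it will do about some of them, but it does not say how the study will learn of them while participants exercise at home. Two things are at stake.

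The first is participant safety. The responses to soreness and orthopedic injury come into play only if someone happens to mention the problem.

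The second is the primary outcome. Feasibility is judged partly from session attendance, self-reported membership use and completion. If a participant stops using the membership because of a sore knee, the count looks the same as loss of interest, and these call for different refinements of the program. The results are meant to shape a manual and a later pilot trial, which would then carry little tolerability information. Analysts cannot reliably recover these data once the 12 weeks are over.

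**Working it through.** The plan states no event rate or safety target, so there is no figure to reproduce. The check is a search of the planned measures, followed by a small illustration.

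**1. Search for an item on injuries or symptoms during the 12 weeks**
- Table 1, acceptability and feasibility rows: focus group, interview, NPS, AIM, IAM, FIM, PCIS, OR4KT, satisfaction ratings, reach, adherence, outcome-measure rates, retention. None is described as asking about injury or symptoms.
- Table 1, other rows: the fidelity checklist concerns recorded sessions. The exercise and sleep log records exercise and sleep. The COVID-19 survey asks only whether COVID-19 affected participation. The remainder are psychosocial, diet, activity, anthropometric and cardiovascular measures.
- Outcome Questionnaires: the Weekly Survey has no such item. The medication review asks about medicines at baseline and week 12.
- Section F: scale ratings, demographics, paired t-tests, qualitative themes and their integration. There is no tolerability summary.

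Checks do exist outside this window: health history, physical examination and PAR-Q+ at screening (C.1), and staff monitoring during the step test.

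**2. Home exercise and step test side by side**

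| Event | Home exercise | Step test |
|---|---|---|
| Soreness | response stated, no planned question | listed as a risk |
| Minor to moderate orthopedic injury | response stated, no planned question | injury listed as a risk |
| Five cardiovascular symptoms | listed as a risk, no action stated in that section | staff monitor, stop and refer |

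**3. Feasibility counts.** Adherence is sessions attended over sessions provided, plus self-reported membership use. Retention is completers over starters. Neither has a field for the reason.

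**4. Live contact.** Table 3 puts group classes in weeks 1, 4 and 8 and individual sessions in weeks 3, 6 and 10. That is 6 of 12 weeks. Weeks 2, 5, 7, 9, 11 and 12 offer only recorded imagery and online access. The session descriptions in Table 2 include no symptom check.

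**5. Illustration of what silence would mean.** Let p be the true proportion of participants affected, s the proportion of affected participants whose event is recorded, and n = 9.
- Chance of recording at least one: 1 − (1 − p·s)^9.
- One-sided 95% upper bound for p when none is recorded: (1 − 0.05^(1/9)) / s = 0.283 / s.

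Both p and s are assumptions.

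| s | p = 10% | p = 20% | p = 30% | Upper bound for p if none recorded |
|---|---|---|---|---|
| 100% | 61% | 87% | 96% | 28.3% |
| 75% | 50% | 77% | 90% | 37.8% |
| 50% | 37% | 61% | 77% | 56.6% |
| 25% | 20% | 37% | 50% | none (0.283 / 0.25 exceeds 1) |

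The 28.3% comes from having 9 participants, and no survey item will lower it. The rise down the last column is what unsystematic collection adds. In practice s would be unknown.

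**The case against.** The strongest reply is that the plan is not silent, and much of that reply stands.

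- **Spontaneous routes exist.** The dietitian sees participants live in six weeks, and the individual sessions plan activity with them. The Weekly Survey has an open field and asks about membership engagement. The week-12 focus group covers feasibility and barriers. A reader might infer that the study could never learn of an injury, or that tolerability cannot reach the feasibility conclusion. The documents do not support that: the routes are unsystematic, not absent. None is described as asking, the focus group comes after the exposure, and it may miss people who dropped out.
- **A clinician route exists.** B.2 requires participants to have, have access to, or be willing to establish care with a clinician for medical issues arising during screening or the interventions. Section D (Screening) adds that the PI will contact a participant if an undiagnosed disease is found. So one cannot say that no provision covers symptoms in home exercise. The exercise section itself states no action for them, and the general provisions do not say how study staff would hear of a symptom.
- **The step-test rule is not a contradiction.** Stopping an observed test has no direct counterpart in home activity, so different handling is reasonable. What remains is that the passages should be read together and reconciled.
- **Unseen material.** Consent pages were removed before review and may tell participants to report problems. That would help safety, but it would not add an item to the measures or a summary to section F.
- **The plan makes no safety-rate claim.** Under Potential Scientific Problems it says that its question is acceptability and feasibility. This is correct, and it is why the table above is only an illustration.

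A reader might also size the gap by the hours of exercise that staff do not observe. That would measure who watches, not who asks, and would be unchanged by better questions. It also needs an average activity level that the documents do not give. Even the description of home exercise as unsupervised by study staff is inferred from remote delivery, and livestream classes may have instructors.

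**Conclusion.** The point holds in a limited form. During the 12-week home-exercise period, the visible protocol neither systematically collects nor summarises the injuries, falls and symptoms that it names as risks. Its responses to soreness and orthopedic injury therefore depend on spontaneous reports, and its adherence and retention counts cannot systematically separate injury-related non-use or dropout from low interest.

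The size cannot be stated as a rate, because no event rate is given. The gap covers all 9 participants and all 12 intervention weeks, or 9 × 12 = 108 person-weeks if everyone completes. An absence of recorded events would mean little: the upper bound runs from 28.3% with full capture to no useful bound at 25% capture. This rests on the assumed capture proportions and on the consent pages containing no structured reporting form.

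It does not show that the trial is unsafe or that the plan lacks any medical provision. It is an inexpensive improvement that should be made before the field trial starts.

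**What to change.** 1. Add two fixed items to the Weekly Survey: any injury, fall or pain that limited activity in the past week, and any of the symptoms listed in section D (Move+ Program and Exercise Prescription). Table 1 gives satisfaction ratings every 3 weeks while Outcome Questionnaires says weekly. State which schedule applies, so that these items are asked every week.
2. Record the reason whenever a participant stops using a component or leaves the study, and add this to the adherence and retention rows of Table 1.
3. Add one descriptive table to F.1 and to the feasibility results: number of participants affected out of 9, type of event, and reasons for stopping.
4. The study team should reconcile B.2, section D (Screening; Move+ Program and Exercise Prescription) and section D (3 Minute Step Test) on how reported symptoms are handled. No clinical rule is proposed here.

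The cost is a few seconds per participant per week, some staff time to read the responses, and one table. The sample size and the other analyses do not change.
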